3. Medicine expenses (Jingsi herbal drink concentrate, please fill in the quantity)	Jingsi herbal drink concentrate (2 packs*30 days*150 people)	0	9,000	0
	Placebo (2 packs*30 days*150 people)	0	9,000	0
	Subtotal			0
4. Subject subsidy	Subject allowance (subsidy)	1,200	150	180,000
	Subtotal			180,000
5. Inspection fee (Please fill in the inspection items and fees)	LC-MS sample processing and analysis, intestinal bacteria analysis	5,000	150	750,000
	Subtotal			750,000
total				1,450,000

E. Summary of the plan in Chinese

Please give an overview of the main points of this project within 500 words, and customize keywords according to the nature of this project, and please write in Chinese.

新冠肺炎患者在痊癒後，約 10% 患者產生長新冠症狀，長新冠症狀中的腹痛、腹脹、腹瀉及便秘源自於腸腦軸失調，腸腦軸失調包含功能性消化不良和腸躁症，常規檢查無明顯異常，由於原因不明但盛行率高，往往對患者的身心健康影響甚鉅。即使腸腦軸失調目前被認為和胃腸道局部發炎和微生物菌相改變有關，但目前西醫治療療效不佳。有鑑於此，許多研究應用中草藥在功能性消化不良，並且達到不錯的療效。淨斯本草飲濃縮液為取得衛福部外銷專用許可證之食品，其成分為艾葉、魚針草、麥門冬、魚腥草、桔梗、甘草、紫蘇葉、菊花等臺灣本土八種能清潤、散寒、宣肺化痰、利濕清熱的中藥草，在臨床試驗登記立案作為輔助新冠肺炎的治療，目前初步發現亦可改善患者腸胃症狀以及憂慮程度。故本研究採雙盲隨機試驗，以淨斯本草飲濃縮液用於客觀檢查皆正常之長新冠症狀-腸腦軸失調患者，評估其治療前後之身心症狀以及腸道菌代謝產物之變化。

關鍵詞：長新冠症狀、腸腦軸失調、淨斯本草飲濃縮液、身心症狀

計畫概述：請概述執行本計畫之目的及可能產生對社會、經濟、學術發展等面向的預期影響性(三百字以內)。

腸腦軸失調(DGBI)包含功能性消化不良和腸躁症為新冠肺炎感染後的腸胃道問題，也是傳統西醫療效值得改善的疾病，淨斯本草飲濃縮液為東部地區研發之中草藥食品，期待淨斯本草飲濃縮液在感染新冠肺炎病毒後改善腸胃道功能以及憂鬱情況的發現能夠用於改善腸腦軸失調(DGBI)之身心症狀。

※此部分內容於獲核定補助後將逕予公開

F. Summary of the plan in English

Please provide an overview of the main points of this project within 500 words, and customize keywords according to the nature of this project, and please write in English.

Dyspepsia refers to chronic or recurrent upper gastrointestinal symptoms. According to the Rome IV criteria, functional dyspepsia (FD) symptoms included meal-related fullness, early satiation, epigastric pain or burning which are unexplained after routine investigation. FD causes substantial psychophysical burden because of its unknown etiology and high prevalence. Although FD is currently associated with local inflammation of the gastrointestinal tract and microbiota alteration, current available treatments for FD are of limited effectiveness. In view of this, many studies have applied Chinese herbal medicine in FD and achieved some therapeutic benefit. The Jing Si Herbal Tea Liquid Packet composed of eight native Taiwanese herbs (wormwood, hickory grass, *Ophiopogon japonicus*, *houltuynia cordata*, platycodon, licorice, perilla leaves, chrysanthemum) has obtained a special export license from the Ministry of Health and Welfare. The Jing Si Herbal Tea Liquid Packet also has been registered in clinical trials as a complementary treatment for COVID-19. The preliminary data demonstrated that the Jing Si Herbal Tea Liquid Packet may improve gastrointestinal symptoms and anxiety in patients with COVID-19. Therefore, this study aims to investigate the impact of the Jing Si Herbal Tea Liquid Packet on psychophysical burden and metabolites of microbiota in patients with FD through a double-blind randomized manner.

關鍵詞： functional dyspepsia; Jing Si Herbal Tea Liquid Packet; psychophysical burden

G. Background and purpose of the research project

Please describe in detail the background, purpose, importance of this research project and the research situation related to this project at home and abroad,
Comments on important references, etc., please write in Chinese format.

Background

Symptoms of the new crown-gut-brain axis disorder (disorders of gut-brain interaction, DGBI)

COVID-19 is raging all over the world. The novel coronavirus recognizes type 2 angiotensin-converting enzyme and infects various cells in the body, including cells in the gastrointestinal tract. About 12%–20% of patients are infected and develop gastrointestinal symptoms. (1, 2) About 10% of patients with COVID-19 will develop symptoms of COVID-19 after recovery, (3) Abdominal pain, bloating, diarrhea and constipation in symptoms of COVID-19 originate from disorders of gut-brain interaction , DGBI). (4) In the upper gastrointestinal tract (upper abdominal pain, abdominal distension), it is called functional dyspepsia, and in the lower gastrointestinal tract (abdominal pain, diarrhea, constipation), it is called irritable bowel syndrome. (5) In a large-scale survey in the United States (more than 100,000 people), it was found that after the COVID-19 epidemic, the incidence of gut-brain axis disorder (DGBI) increased by 75% compared with before the epidemic. (6) Disorders of the gut-brain axis (DGBI) include functional dyspepsia and irritable bowel disorder. At present, there is no clear pathogenesis and standard treatment. The consensus is to use the Roman diagnostic criteria, evaluate by questionnaire, and exclude other organic diseases. disease to diagnose. (5) The possible mechanisms of gut-brain axis disorder (DGBI) include local inflammation of the gastrointestinal tract, infiltration and activation of allergic cells, mucosal defects, changes in microbial flora, and hypersensitivity of viscera. (7) In terms of the microbial flora of the brain-gut axis, the metabolites of intestinal bacteria are regarded as the key to influence, among which short-chain fatty acids (SCFA) are regarded as good metabolizers As a product, when carbohydrates are fermented, anaerobic bacteria will produce many short-chain fatty acids (SCFA) in the distal small intestine and colon, which are composed of 1-6 carbon atoms, and the main three metabolic compounds are acetic acid (Acetate), Propionate and Butyrate. Short-chain fatty acids (SCFA) have been shown in research to have anti-inflammatory, anti-oxidant, anti-diabetic, anti-cancer and antibacterial effects. When the bacterial phase changes, the concentration of short-chain fatty acids may change accordingly and affect human physiological responses. When the intestinal flora is out of balance, a variety of bad metabolites will be produced: Trimethylamine N-oxide, TMAO (derived from L-Carnitine or Choline), indoxyl sulfate (derived from Tryptophan) and p-cresyl sulfate (derived from Tyrosine), etc. (8)

Changes in the bacterial phase of the new crown symptoms

SARS-CoV-2 infection caused significant changes in the intestinal flora of patients. The number of

potential pathogens in the patient's body increases, and the antibiotic treatment also reduces the beneficial bacteria.⁹ Hazan et al. (2022) showed reduced gut bacterial diversity in infected individuals, with reduced numbers of Bifidobacterium, Faecalibacterium, and Roseburium.¹⁰ At six months post-infection, the intestinal bacterial diversity of the patients was still significantly low.¹¹ In addition to reduced diversity, these symptomatic patients had lower numbers of anti-inflammatory bacteria such as Faecalibacterium prausnitzii, Eubacterium rectale, Bifidobacterium adolescentis, and potential pathogens such as Rothia, Erysipelatoclostridium, Ruminococcus gnavus in the gut three months after infection. , Ruminococcus torques, and Bacteroides dorei are more.¹² Su et al. (2022) studied the dysbiosis caused by post-acute COVID-19 syndrome and found that there were more potential pathogens such as Erysipelatoclostridium ramosum and Ruminococcus gnavus, and beneficial bacteria Bifidobacterium adolescentis, B. pseudocatenulatum) decreased.¹³ These evidences show that the intestinal flora has not fully recovered from the imbalance during infection, and is still in a state of low diversity and favorable pathogens, which can continue to cause immune responses in the intestine. Functional dyspepsia is also thought to be caused by increased permeability of the intestinal wall of the small intestine, allowing intestinal microbial metabolites to infiltrate the tissues and activate the immune system.¹⁴

In both functional dyspepsia and irritable bowel disorder, there is marked dysbiosis in the gut. Bacterial changes in patients with functional dyspepsia include decreased numbers of Bacteroidetes (Prevotellaceae) and increased numbers of Proteobacteria, Firmicutes (Streptococcus and Clostridia) and Bifidobacteria.¹⁵ Bacterial changes in IBD included increased Clostridia (increased Ruminococcus but decreased Faecalibacterium), increased Lactobacillus and Streptococcus within the phylum Firmicutes, increased Bacteroides, and decreased Bifidobacteria.¹⁶ After synthesis, it can be seen that the changes in the gut-brain axis disorder are mainly due to the replacement of Bacteroidetes by Firmicutes, while the changes in the number of Proteobacteria and Bifidobacteria are inconsistent.

Jing Si Herbal Tea Liquid Packet

The ingredients of Jing Si Herbal Tea Liquid Packet are mugwort leaves, houttuynia cordata, Ophiopogon japonicus, Houttuynia cordata, Campanulaceae, licorice, perilla leaves, chrysanthemum and other eight native Taiwanese herbs that can clear away moisture, dispel cold, relieve lungs and resolve phlegm, and clear away dampness and heat. Chinese medicinal herb, current research has found that it can block the combination of the new coronavirus and cells, and can also reduce cell penetration and block the virus from penetrating cells, while targeting wild-type and mutant viruses D614G, B.1.1.7, 501Y.V2 Carrying out animal studies, it was found that Jing Si Herbal Tea Liquid Packet can reduce the ability of 60 to 70% of the virus to infect the upper respiratory tract, lung, heart, and intestine of mice and reduce the expression of FKBP51, a protein related to depression, by 40%. The effect of using Jing Si Herbal Tea Liquid Packet to help reduce the amount of virus and systemic anti-inflammatory effect in patients with COVID-19. (9) In our

Version date : (Version 3, 11/10/2022)

ongoing clinical study, for functional dyspepsia (FD) patients, Jing Si Herbal Tea Liquid Packet can improve symptoms in 75% of patients, compared with only 33% of placebo.

Purpose

A double-blind randomized trial was conducted to investigate the improvement of Jingsi Bencao decoction concentrate on the physical and mental symptoms of gut-brain axis disorder (DGBI) and the changes in intestinal flora after COVID-19.

Importance

Gut-brain axis disorders (DGBI), including functional dyspepsia and irritable bowel syndrome, are gastrointestinal problems after COVID-19 infection. They are also diseases that are worthy of improvement in the efficacy of traditional Western medicine. The discovery that Jingsi Bencao Drink Concentrate improves gastrointestinal function and depression after infection with the new coronavirus can be used to improve the physical and mental symptoms of gut-brain axis disorder (DGBI).

※If there are not enough fields, please copy by yourself.

H. Research methods, steps and implementation progress

1. Please describe in detail the research methods and reasons used in this project.
2. Estimated possible difficulties and solutions.
3. If it is a continuous plan, the research progress report or primary data of the previous year should be attached at the same time.
4. Please write in Chinese format.

1. Subject acceptance and exclusion conditions

This study is a prospective study, which is expected to last for one year. It is planned to recruit 150 subjects with gut-brain axis disorder (DGBI) three months after being infected with new coronary pneumonia: 75 of them Functional dyspepsia (FD) subjects and 75 irritable bowel syndrome (IBS) subjects.

Subject inclusion conditions (Inclusion criteria)

1. Age between 20-70 years old.
2. Those who meet the definition of functional dyspepsia (FD).
(Functional dyspepsia (FD) is chronic (once a week, lasting at least three months, at least six months before the first symptom) upper gastrointestinal symptoms (any of the following): postprandial abdominal distension, easy to feel full, Epigastric pain or burning sensation in the upper abdomen, and no symptoms of gastrointestinal bleeding or significant weight loss, no abnormality after upper gastrointestinal endoscopy).
3. Those who meet the definition of irritable bowel syndrome (IBS).
(Irritable bowel syndrome (IBS) is chronic (once a week, lasting for at least three months) lower gastrointestinal symptoms: abdominal pain combined with diarrhea or constipation, and no symptoms of gastrointestinal bleeding or significant weight loss, no abnormalities after colonoscopy) .
4. Be conscious and willing to sign the subject's consent form.

Subject Exclusions (Exclusion criteria)

1. Abnormal liver and kidney function;
2. Abnormal blood tests and thyroid abnormalities;
3. Have received surgery on the digestive tract;
4. Abnormal upper gastrointestinal endoscopy;
5. Abnormal colonoscopy;
6. Antibiotics are being used for infectious diseases;
7. Pregnant or breastfeeding women;
8. Suffering from heart, liver, or kidney failure;
9. Physical weakness, allergies, asthenia and cold constitution and chronic diseases.

[figure not shown]
2. Experimental process

150 subjects with gut-brain axis disorder (DGBI) three months after being infected with new coronary

Version date : (Version 3, 11/10/2022)

pneumonia will be recruited in the outpatient department of gastroenterology, including 75 subjects with functional dyspepsia (FD) and 75 subjects with irritable bowel syndrome (IBS) subjects; qualified subjects will receive blood and feces sampling and complete physical and mental symptom assessment (sleep habits questionnaire, anxiety questionnaire, stress questionnaire, gastrointestinal symptoms questionnaire, and irritable bowel syndrome questionnaire) before treatment, and then according to the double-blind random allocation method, the computer generated garbled characters, and assigned Jing Si Herbal Tea Liquid Packet or placebo according to the coding sequence, and the research assistant gave Jing Si Herbal Tea Liquid Packet or placebo, Host and recipients None of the subjects knew what the content of the assignment was. The experimenters took Jing Si Herbal Tea Liquid Packet or placebo in the first month, and after the end of the month, they received blood and stool tests and complete physical and mental symptom assessment (sleep habits questionnaire, anxiety questionnaire, stress questionnaire), gastrointestinal symptom questionnaire, and irritable bowel syndrome questionnaire), the laboratory will conduct pre- and post-test analysis of LC-MS and intestinal bacteria, and then conduct a cross-test. The original placebo will take Jing Si Herbal Tea Liquid Packet in the second month, previously taking Jing Si Herbal Tea Liquid Packet will take a placebo in the second month, after the end of the second month, do the third complete physical and mental symptom assessment (sleep habits questionnaire, anxiety questionnaire, stress questionnaire, digestive tract Symptom Questionnaire, Irritable Bowel Disorder Questionnaire), the test is completed.

Research flow chart

3. Questionnaire

The questionnaire items included sleep habits questionnaire, anxiety questionnaire, stress questionnaire, gastrointestinal symptoms questionnaire, and irritable bowel syndrome questionnaire. The details of the questionnaire are attached.

4. Collection, preservation, transportation and DNA extraction of feces

Fix the collection box on the toilet lid, discharge fresh feces into the collection box, then screw the lid tightly and place it in a zipper bag within 4 hours or in a -4°C refrigerator within 24-48 hours Sent to the laboratory for sub-packaging, and then refrigerated in a -80°C refrigerator. Thaw when the DNA is extracted, the extraction process includes the following steps sample homogenization, cell lysis, non-DNA material removal and DNA purification.

5. Gut microbiota sequencing and community analysis

In this study, 16S rDNA massively parallel sequencing will be used to analyze the composition of gut bacteria. 0.25 g of stool samples were pooled for DNA extraction with the QIAmp PowerFecal Kit (Qiagen, Hilden, Germany). The purified DNA was PCR'd with primers for 341F and 805R to amplify the V3-V4 fragments of the 16S rRNA gene, and the barcode was sent to the manufacturer for library building. The Illumina MiSeq platform was used for next-generation pair-end sequencing. Sample 30000 reads. After the sequence obtained by the manufacturer was screened for high-quality fragments by Mothur and Usearch software, the bacterial phase composition and taxonomic status of each sample were calculated. The taxonomic status of each sequence was determined by comparing the Mothur software with the SILVA sequence database. The investigators will use Microbiome Analyst R and other suitable R programming language packages to perform cluster analysis and network analysis of bacterial composition.

6. Stool and Blood LC-MS Analysis

I. Plasma sample collection and preparation :

Whole blood was collected in Vacutainer K2E-EDTA (BD Diagnostics, Franklin Lakes, NJ, USA) blood collection tubes. The collected whole blood samples were then transferred to 15 mL containing Ficoll-paque PLUS medium [whole blood (all blood)/ Ficoll-paque PLUS medium = 4/3 (volume ratio v/v)] (GE Healthcare Life Sciences, Pittsburgh, PA, USA) and centrifuge (3000 rpm, 30 min) at room temperature. After centrifugation, the plasma (plasma) supernatant that was successfully layered was collected and distributed into sterilized 1.5 mL microcentrifuge tubes (Eppendorf), and glacial acetic acid with a concentration of 1 N and a volume of 1% was added.) aqueous solution to prevent the degradation of the analyte in plasma. Plasma is stored in a freezer at -80°C, and the storage period does not exceed 1 year.

II. Previous processing method of Lipophilic Substances :

Thaw the plasma sample at room temperature for 10-20 minutes, then transfer 100 μ L of plasma to a new 1.5 mL microcentrifuge tube. Add the internal standard (internal control, 13C-PA) first, then add methanol 3 times the volume of plasma for deproteinization, and let it stand at room temperature for about 15-20 minutes. Then centrifuge the rested microcentrifuge tube (3,000 rpm, 10 min, 4 $^{\circ}$ C), and transfer the supernatant to the corresponding small glass test tube. Move the glass test tubes to a nitrogen blowing system, dry the samples through a nitrogen flow, and then add 100 μ L of chloroform (Chloroform) to each sample for redissolution. A filtration extraction system was set up, and solid phase extraction columns [Solid phase extraction (SPE) columns (Strata-X-C 33 μ m polymeric strong cation 60 mg/3 mL, Phenomenex, Torrance, CA, USA)] were used for extraction. Add 1.0-1.5 mL of n-hexane (hexane) solution to the erected column to activate the column, and use a vacuum pump to pump positive pressure for about 20-30 seconds. Replace the glass test tubes that have been filled with n-hexane solution under the filter extraction system, and then add the samples to the activated column in sequence. Add 1.0-1.5 mL of ethyl acetate (ethyl acetate) for vacuum extraction for about 30-45 seconds, and transfer the sample extracted with ethyl acetate to a nitrogen blowing system to dry it. Redissolve the sample with 100 μ L of methanol, and finally transfer the reconstituted sample to a liquid chromatography-mass spectrometer (LC-MS) vial equipped with insert, and prepare for analysis on the machine with an injection volume of 30 μ L per needle .

III. Hydrophilic Substances before the processing method :

There are two extraction methods for such compounds, namely traditional methanol extraction (Traditional deproteinized extraction) and SLE column extraction (SLE column extraction). First, place the plasma sample at room temperature to thaw for about 10-20 minutes. After the thawing is complete, take 100 μ L to a new 1.5 mL microcentrifuge tube (two tubes of 100 μ L are required for each sample). Plasma samples were deproteinized by adding methanol at a volume ratio of 3 times or adding an equal volume of 50 mM sodium phosphate dibasic heptahydrate (Sodium phosphate dibasic heptahydrate) and evenly mixed. Set up the SLE column filtration system and sample test tube, put the sample mixed with 50 mM disodium hydrogen phosphate hydrate into the column, turn on the vacuum pump to filter and extract, wait for about 3 minutes, then add 1.2-1.5 mL of acetic acid Ethyl esters are used for dike flushing. In addition, for the methanol deproteinized group, after waiting for about 20 minutes, they were centrifuged (3,000 rpm, 10 min, 4 $^{\circ}$ C), and then the supernatant was taken out into the corresponding glass test tube. The samples with two different treatment methods were put into the nitrogen blowing system for drying and concentration. For the group undergoing deproteinization, add 300 μ L of methanol to redissolve, and filter with MILLEX GP 0.45 μ M PVDF filter (Millipore), and discharge the liquid into the LC-MS special sample bottle loaded with insert; For the group extracted by the column, 100 μ L of methanol was added for back-dissolution and reconstitution, and it was put into the LC-MS special sample bottle loaded with insert, ready for analysis on the machine.

d. LC-MS Analysis Conditions (Liquid Chromatography Mass Spectrometer) :

LC-MS condition I : Used to analyze Lipophilic Substances

LC-MS condition II : Used to analyze Hydrophilic Substances Substances)

Table 1. LC-MS analysis conditions:

LC conditions			
HPLC system	Waters Alliance e2695	Injection volume	30 μ L
Runtime	60.0 min (I) 18.0 min (II)	Column	Phenomenex Luna C18(2) (250 x 4.6 mm, 5 μ m)
Flow rate	0.6 mL/min (I) 0.8 mL/min (II)	Column temp	35°C (I) 40°C (I)
Condition I (Lipophilic Substances)			
Mobile phase A		Mobile phase B	
60:40 Acetonitrile:ddH ₂ O with 9.2 mM Ammonium acetate (NH ₄ CH ₃ CO ₂) (pH 8.85)		90:10 Isopropanol:Acetonitrile with 9.2 mM Ammonium acetate (NH ₄ CH ₃ CO ₂)	
Time (min)	%A	%B	Curve
Initial	85	15	6
8.0	70	30	6
10.0	52	48	6
44.0	18	82	6
46.0	1	99	6
48.0	1	99	6
48.4	85	15	6
60.0	85	15	6
Condition II (Hydrophilic Substances)			
Mobile phase A		Mobile phase B	
0.1% Formic acid in 99.9% ddH ₂ O		0.1% Formic acid in 99.9% MeOH	
Time (min)	%A	%B	Curve
0	95	5	6
14	30	70	6
16	30	70	6
18	50	50	6
MS conditions			
Detector	Waters ACQUITY QDa (Performance)		
Ionization mode	ESI Negative (I); ESI Negative and Positive (II)		
Capillary voltage	Default (0.8 kV)		
Probe temp	Default (600°C)		
Cone voltage	20V(I); 15V(II)		
Sampling rate	8 Hz		
Full scan	250-600 m/z for Negative (I); 70-600 m/z for Negative or Positive		
SIR	See Table 2 - "Molecular Ions (m/z)"		

e. Method validation :

Including Limits of detection, LOD and Limits of quantitation, LOQ, Calibration curve, Recovery, accuracy and precision, Intra-assay, accuracy and precision and Inter-assay precision and accuracy of each test substance.

Table 2. LC-MS analysis Standard List:

	Molecular ion (m/z)	Ion source mode

Lipophilic Substances			
Short Chain Fatty acids (SCFAs)	Acetate (2:0)	42.0+153 (3NPH)	ESI Negative
	Propionate (3:0)	57+153 (3NPH)	ESI Negative
	Butyrate (4:0)	72+153 (3NPH)	ESI Negative
Long Chain Fatty acids	Palmitic acid, PA (16:0)	255.1	ESI Negative
	Stearic Acid, SA (18:0)	283.2	ESI Negative
	Palmitoleic Acid, POA (16:1)	253.2	ESI Negative
	Oleic Acid, OA (18:1)	281.2	ESI Negative
Fatty acid esters of hydroxy fatty acids (FAHFAs)	Palmitoleic Acid Ester of 9-Hydroxystearic Acid (9-POHSA)	535.5	ESI Negative
	Oleic Acid Ester of 9-Hydroxystearic Acid (9-OAHSA)	563.5	ESI Negative
Internal standards			
	[¹³ C ₁₆]- Palmitic acid (IS1)	271.4	ESI Negative
Hydrophilic Substances			
Methionine cycle	L -Methionine (L -Met)	150.1	ESI Positive
	S -adenosyl- L -methionine (SAM)	399.0	ESI Positive
	S -adenosyl- L -homocysteine (SAH)	385.0	ESI Positive
	L -Homocysteine (L -Hcy)	136.1	ESI Positive
	Methylmalonic acid (MMA)	117.1	ESI Negative
Antioxidants	Ascorbic acid (AA)	174.9	ESI Negative
Nutrition index	3-Methyl- L -histidine (3-MH)	170.0	ESI Negative
Fatty acids carrier	L -Carnitine (L -Car)	162.1	ESI Positive
	Acetyl- L -Carnitine (ALC)	204.0	ESI Positive
	Propionyl- L -Carnitine (PLC)	218.0	ESI Positive
Nephrotoxin	Trimethylamine N -oxide (TMAO)	76.0	ESI Positive
	Indoxyl Sulfate (InS)	211.9	ESI Negative
	p -Cresyl sulfate (pCS)	187.0	ESI Negative
Internal standards			
	d3- L -Methionine (d3- L -Met) (IS2)	153.1	ESI Positive
	d9-Trimethylamine N -oxide (d9-TMAO) (IS3)	85.0	ESI Positive

7. Jing Si Herbal Tea Liquid Packet

In this experiment, Jing Si Herbal Tea Liquid Packet was used. Its ingredients are eight kinds of native Taiwan species, such as mugwort leaves, hinoki, *Ophiopogon japonicus*, *Houttuynia cordata*, bellflower, licorice, perilla leaves, and chrysanthemum. , Dampness-clearing and heat-clearing herbs, take Jing Si Herbal Tea Liquid Packet 15 ml once a day in the morning and evening.

8. Statistical Analysis

Continuous variables were expressed as mean and standard deviation if they were normally distributed; if they were not normally distributed, they were expressed as median and interquartile range. The treatment effect is presented by the improvement percentage of the sleep habits questionnaire, depression questionnaire, anxiety questionnaire, stress questionnaire, gastrointestinal symptoms questionnaire, and irritable bowel syndrome questionnaire before and after treatment, and the curative effect of Jingsi Bencao Drink Concentrate and placebo is expressed as the chi-square by the improvement percentage Chi-squared test comparison, P value less than 0.05 was considered statistically significant difference, the statistical analysis software used was SPSS 19 for Windows (SPSS, Inc, Chicago, IL, USA).

9. Sample Size Estimation

According to our ongoing research, it is estimated that the efficacy of Jing Si Herbal Tea Liquid Packet for functional dyspepsia (FD) is 75%, while the efficacy of placebo is 33.3%. It is estimated by α -error 0.05; β -error 0.20, at least 100 subjects are required to be admitted, and taking into account that the subjects may withdraw and fail to complete the trial successfully, the estimated number of subjects admitted in this study is 150.

10. Possible difficulties and solutions

Possible difficulties: According to our current research, the effect of placebo on functional dyspepsia (FD) can reach 33.3%, so if the investigators want to prove that Jing Si Herbal Tea Liquid Packet has a positive effect on patients with new coronary pneumonia three months after infection Gut-brain axis dysregulation (DGBI) had to be statistically significantly greater than placebo to have a significant effect.

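### FD and IBS have fixed quotas of 75 each, but no stratification or blocking by diagnosis is described and the analysis does not account for it; this leaves the month-1 flora and metabolite comparison open to avoidable chance imbalance.

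*Protocol*

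**What the plan says.** Protocol H.1 gives FD and IBS separate definitions. H.2 repeats the quotas: "including 75 subjects with functional dyspepsia (FD) and 75 subjects with irritable bowel syndrome (IBS) subjects".

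H.2 describes allocation once, for everyone, as random and double-blind. Codes come from a computer, and subjects are "assigned Jing Si Herbal Tea Liquid Packet or placebo according to the coding sequence". It mentions no strata, blocks or lists by diagnosis, and no allocation ratio.

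The design is a crossover: "The original placebo will take Jing Si Herbal Tea Liquid Packet in the second month", and the other group changes to placebo. Blood and stool are described before treatment and at the end of month 1. For the end of month 2, H.2 lists only the questionnaires.

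H.8 compares improvement percentages between the herbal product and placebo by a chi-squared test and mentions no adjustment for diagnosis. H.9 plans on rates of 75% and 33.3%. The first is stated for FD only: "the efficacy of Jing Si Herbal Tea Liquid Packet for functional dyspepsia (FD) is 75" (per cent).

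**The concern.** The protocol itself treats diagnosis as something that matters. It defines the two conditions separately, fills them to separate quotas, and has planning rates for one of them only. The background in section G also reports different flora patterns. Bifidobacteria are said to rise in FD and to fall in the other disorder (printed as IBD, in a paragraph about functional dyspepsia and irritable bowel).

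Diagnosis is therefore a plausible predictor of the outcomes, and it is known before allocation. If neither the allocation nor the analysis uses it, the FD/IBS mix may differ by chance between the two sequences. This matters most for flora and metabolites. The stated purpose includes changes in intestinal flora, and as the sampling is described, products can be compared on these measures only between subjects at month 1. At stake are some precision, and how readily a reader will believe a month-1 difference if the sequences turn out to differ in diagnosis.

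**Working it through.** The protocol gives no figure for balance by diagnosis, so there is none to reproduce. Its minimum of 100 subjects is a separate matter. At 75% v 33.3%, two-sided 0.05 and 80% power, the usual formula gives 22 per arm (44 in total), or 26 per arm (52) with continuity correction. So 100 is not reproduced, but it is no shortfall for a pooled comparison.

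**Inputs.** 75 FD and 75 IBS (H.1, H.2); 75% and 33.3% (H.9). Assumed because not stated: 1:1 allocation and a two-sided test.

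**1. FD subjects in one sequence**

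- Simple allocation, Binomial(75, 0.5): SD = √(75 × 0.5 × 0.5) = 4.3; 95% range 29 to 46.
- One list balanced 75/75 overall, Hypergeometric(150, 75, 75): SD = √(75 × 0.5 × 0.5 × 75/149) = 3.1; 95% range 32 to 43.

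| Split of the 75 FD subjects, at least as uneven as | Simple | Balanced 75/75 overall |
|---|---|---|
| 33/42 | 36% | 19% |
| 32/43 | 25% | 10% |
| 31/44 | 17% | 5% |

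**2. Difference in FD share between sequences** (75 per sequence)

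- SD = 2 × 3.07/75 = 0.082; 95% limit = 1.96 × 0.082 = 0.161, about 16 points.
- A 33/42 split gives 42/75 − 33/75 = 0.12, or 12 points.

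**3. Effect on an unadjusted month-1 comparison**

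Shift = difference in FD share × difference between FD and IBS in the outcome.

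- The protocol does not give the FD/IBS difference in response. Assuming 10 to 30 points, the 95% limit gives 0.16 × 10 = 1.6 to 0.16 × 30 = 4.8 points. A 33/42 split gives 1.2 to 3.6 points.
- The planned difference is 75 − 33.3 = 41.7 points.
- For flora and metabolites no effect size is given. By the same formula the shift is at most about 16% (95% limit) of the FD/IBS difference in that measure. If change from baseline is analysed, only a difference in change counts.

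**4. Power within one disease at month 1** (75% v 33.3%, 75 subjects)

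| Split | Power | Variance relative to 37/38 |
|---|---|---|
| 37/38 | 96.6% | 1.00 |
| 31/44 | 96.2% | 1.03 |
| 29/46 | 95.9% | 1.05 |

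The loss is 96.6 − 95.9 = 0.7 points at the edge of the simple-allocation range. For IBS this borrows the FD rates.

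**5. What separate lists would do**

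- Unblocked lists leave each disease at Binomial(75, 0.5), still 29 to 46.
- With permuted blocks, the difference between sequences within a disease never exceeds half a block. As 75 is odd, 37/38 is the best possible split.

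**The case against.** The strongest reply is that the protocol is silent rather than wrong. A reader might infer from H.2 that all 150 subjects come off one list, but that rests on the singular noun and the absence of any mention of strata. The text does not exclude lists by diagnosis, the flow chart is not available to check, and such details are often kept in a randomisation plan. This stands: the point can be only that no stratification is described.

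Second, the crossover does most of the work. Each completer takes both products, so in a within-subject comparison of the questionnaires diagnosis is balanced between products. Imbalance could enter there only through withdrawals or period and carryover effects. This also stands, and it confines the point mainly to month-1 comparisons. It does not help flora and metabolites, for which no sample after month 2 is described. Nor does H.2 or H.8 set out how those measures will be compared between products, so the harm is to a comparison that the stated purpose implies, not one that is spelled out.

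Third, a reader might infer that the comparison is biased, or that each disease has its own questionnaire and so its own endpoint. Neither is supported. Randomisation keeps the test valid and chance imbalance is covered by its error rate. All subjects complete the same set of questionnaires.

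Finally, adjustment could be left to an analysis plan. That is true of the analysis but not of the list, which has to be built before the first subject is allocated.

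**Conclusion.** The point holds as a low-cost improvement, not as an error. The quotas are fixed by diagnosis, no stratification or blocking by diagnosis is described, and the stated test ignores diagnosis. The FD count in one sequence can therefore run from 29 to 46 (simple allocation) or 32 to 43 (balanced overall), and the month-1 flora and metabolite comparison does not have the crossover's protection.

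The size is modest: under one point of within-disease power, and a shift of at most about 1.6 to 4.8 points in a pooled month-1 response difference, against 41.7 planned. Those shifts rest on an assumed FD/IBS gap of 10 to 30 points and on the 95% limit of imbalance. All figures assume 1:1 allocation. The gain is in precision and balance; there is no bias to correct. It would also be wrong to conclude that separate lists alone would settle it, because without blocks the imbalance within each disease is unchanged.

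**What to change.** - In H.2, specify one concealed permuted-block list for each diagnosis, 1:1 by sequence, with the block size withheld from those who enrol subjects.
- In H.8, stratify or adjust for diagnosis. For month-1 improvement percentages, a Cochran-Mantel-Haenszel test stratified by diagnosis can replace the plain chi-squared test. For month-1 flora and metabolites, include a diagnosis term.

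The cost is a change to code generation and slightly more analysis. Diagnosis is already established before allocation, and no subjects, visits or samples are added. The list must be changed before the first allocation; if allocation has begun, the analysis change can still be made.
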